**508 3.1 Randomization Groups**

509

510 Each patient will be randomly assigned to one of two treatment groups in a 1:1 ratio:

- 511 1. Two (2) hours of daily patching combined with 30 minutes of daily near activities at  
512 home, 30 minutes of daily at-home active vision therapy, and a weekly 45 minute in-  
513 office active vision therapy session.
- 514 2. Two (2) hours of daily patching combined with 30 minutes of daily near activities at  
515 home, 30 minutes of daily at-home control vision therapy, and a weekly 45 minute in-  
516 office control vision therapy session.

517

518 Spectacle wear will be continued if prescribed. Patients wearing contact lenses must be switched  
519 to spectacles prior to enrollment for the duration of the study.

520

521 Weekly Office Visits: Each patient randomized into the study will be seen on a weekly basis for  
522 administration of treatment for 16 weeks. At each office visit, the patient will be queried  
523 regarding diplopia and visual acuity in each eye will be measured using the eETDRS protocol.  
524 Each group will receive 45 minutes of vision therapy activities dependent upon their group  
525 assignment.

526

527 Daily patching and at-home vision therapy will be continued through the 17 week masked  
528 examination.

**529 3.1.1 Measurement of Visual Acuity**

530 Prior to each in-office therapy session the vision therapist (or other ATS certified visual acuity  
531 tester) will measure the visual acuity of each eye using the eETDRS protocol (*the protocol for*  
532 *conducting the visual acuity testing is described in the ATS Testing Procedures Manual*). The  
533 person completing the visual acuity measurement for in-office therapy sessions will not be  
534 required to be masked to the patient's treatment assignment.

**535 3.1.2 Sequencing of In-Office Active Vision Therapy**

536 There are three categories of active vision therapy activities. The instructions to the therapist for  
537 all therapy procedures will be specified in the Manual of Procedures. These instructions will  
538 include a list of specific goals which should be met for each procedure before a patient can  
539 proceed from one phase to the next. The three categories of therapy are:

- 540 • Accommodation
- 541 • Anti-Suppression
- 542 • Vergence

543

544 The amount of time the patient wears a patch during the in-office therapy session will be  
545 dependent upon the category and phase of therapy he/she is performing at the weekly office visit.

**546 3.1.3 At-Home Vision Therapy for Active Group**

547 The patients randomized to the active arm of the study will also perform 30 minutes of  
548 regimented vision therapy and 30 minutes of near activities. This home therapy will be  
549 completely computer based. The two programs that will be assigned to the patients in this group  
550 are the Home Therapy System and the Amblyopia iNet Program.

551

552 The Home Therapy System program will have therapy for vergence. The Amblyopia iNet  
553 Program will include activities for eye-hand coordination, tracking, and visual discrimination.  
554 Home VT is performed while wearing the patch. The exception to this is when the patient is  
555 using the HTS software, which is performed without the patch. See section 3.2 for further  
556 discussion on near activities.

#### 557 **3.1.4 In-Office Control Vision Therapy**

558 The control vision therapy will be structured based on weekly schedules. Each week patients  
559 will perform the control therapy procedures as described in the Manual of Procedures.

560  
561 During the control vision therapy sessions the patient will not wear a patch. (Note: the control  
562 vision therapy patients will be instructed to patch for 2 hours and perform 1 hour of near  
563 activities while patched at home on the day of the office visit. Active vision therapy patients will  
564 be instructed to patch for 1 hour at home and perform no near activities or vision therapy in order  
565 to have similar amounts of patching times between the groups.)

#### 566 **3.1.5 At-Home Control Vision Therapy**

567 Patients in the control group will be assigned 1 hour of near activities each day which will  
568 include 30 minutes of computer activity with the study specific computer program. These  
569 activities will be performed while patients are wearing their patches. See section 3.2 for further  
570 discussion on types of near activities, and the Manual of Procedures for further detail on the at-  
571 home computer activities and study specific computer program.

#### 572 **3.1.6 Reporting of Information About Therapy Sessions**

573 After each therapy session, the site will complete a checklist specifying the therapy completed.

#### 574 **3.1.7 Initial In-Office Therapy Visit**

575 The initial in-office therapy visit must be scheduled within 10 days of randomization.

576 Scheduling on the day of randomization is permitted.

577  
578 Study treatment commences on the day of the first in-office vision therapy session. At the end of  
579 the session, patches and the at-home vision therapy software should be given to the patient. The  
580 patient and parent are instructed in their use and given a copy of the treatment instruction sheet.  
581 They are also given a calendar on which to record the amount of time spent patching and using  
582 the home VT software each day.

583  
584 Patients in the active group should be instructed to patch 1 hour that day. No near activities or  
585 home VT are completed that day. This is the same as other days on which an in-office therapy  
586 visit is completed.

587  
588 Patients in the control group should be instructed to patch 2 hours that day and perform 1 hour of  
589 near activities while patched. No (control) home VT is completed that day. This is the same as  
590 other days on which an in-office visit is completed.

591  
592 Both treatment groups are instructed to patch 2 hours and perform 1 hour of near activities of  
593 which ½ hour should be spent using the at-home VT software (either active or control software)  
594 starting the day after the 1st in-office treatment visit.

### 595 **3.2 Patching and Near Activities on Days When an Office Visit is NOT Scheduled**

596  
597 Each patient, regardless of treatment assignment, is prescribed 2 hours of daily patching at home  
598 combined with 1 hour of near activities (including 30 minutes of home-based active or control

599 vision therapy according to treatment group) on days when an office visit is not scheduled. The  
600 prescription of 2 hours daily patching at home must be continued through the 17 week masked  
601 examination. No increase in amount of daily patching is permitted.

602  
603 Patching will be performed using commercially-available patches, which will be provided by the  
604 study.

- 605 • If skin sensitivity occurs, an alternative brand of patch will be provided. If no skin patch  
606 is tolerated, a felt “Patch-Works” type patch will be placed on the lens of glasses over the  
607 sound eye; if glasses are not prescribed, then plano glasses will be provided.

608  
609 The following instructions will be given to the parent:

- 610 • The 2 hours of patching should be continuous.
- 611 • If the child falls asleep while wearing the patch, this time should not be counted as  
612 patching time.

613  
614 Near activity tasks may include any of the following activities:

- 615 • Crafts, coloring, tracing, cutting out objects, dot-to-dot connecting, ‘fill in the symbols’,  
616 ‘symbol sequence’, or other activities requiring eye-hand coordination
- 617 • Hidden pictures and word finds
- 618 • Video games (e.g. Game Boy)
- 619 • Computer/internet
- 620 • Written homework
- 621 • Reading
- 622 • Building models, knitting, stringing beads

623  
624 Accommodative therapy with ophthalmic lenses may NOT be performed as a “near activity.”

625  
626 A list of these activities will be given to the parents of children enrolled in both treatment groups.

627  
628 In addition to these general near activities, patients in the active and control vision therapy group  
629 will be assigned 30 minutes of at-home vision therapy. These 30 minutes will be included in the  
630 requirement for 1 hour of near activities to be completed while patched. The protocol for at-  
631 home vision therapy is specified in the Manual of Procedures.

### 632 **3.2.1 Patching and Near Activities at Home on the Day of the Weekly In-Office Session**

633 In order to equalize patching time between the two groups the following changes to the patching  
634 schedule will be made on the days of an in-office visit:

- 635 • Active Vision Therapy Group: After the weekly in-office vision therapy session the child  
636 will be instructed to wear the patch for only 1 hour at home that day and not to do any of  
637 the near activities (this includes not doing the at-home computer activities). The child  
638 will return to his/her normal schedule the next day.
- 639 • Control Vision Therapy Group: After the weekly in-office control session the child will  
640 be instructed to wear the patch for 2 hours with 1 hour of near activities as usual. The  
641 child will be instructed to skip the at-home computer activities that day. The child will  
642 return to his/her normal schedule the next day.

643

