### 1.2 Rationale for the Study

142  
143  
144  
145  
146  
147  
148  
149  
150  
151  
152  
153  
154  
155  
156  
157  
158  
159  
160  
161

Patching and atropine have been traditionally used for the improvement of visual acuity in children with amblyopia. Previous studies have shown that these methods of treatment are effective in young children with functional amblyopia. More recently ATS3[1], a randomized clinical trial of 507 children ages 7-<18, found that part-time patching combined with atropine and near activities improved visual acuity by two or more lines in 53% of the 7 to 12 year olds compared to 25% for optical correction alone. For the 13 to 17 year olds, part-time patching and near activities improved visual acuity by 2 or more lines in 25%, compared to 23% for optical correction alone. While it appears that patching and/or atropine, combined with near activities, can improve visual acuity in some patients ages 7-<18, most patients in the study were left with residual visual acuity deficits. To further improve visual acuity and binocularity in children with amblyopia some eye care providers augment these traditional therapies with vision therapy. Vision therapy is prescribed initially if there is moderate amblyopia with stereopsis. Vision therapy can be added to the treatment regimen once the patient has reached moderate levels of vision loss with stereopsis or if the patient is not responding to the current treatment and still has moderate amblyopia. It is thought that the best candidates for this type of therapy are those children with a minimum level of stereopsis (at least 800") and without constant strabismus. Those children with no stereopsis would not be able to perform the activities in the later stages of therapy utilizing binocular vision.

162  
163  
164  
165  
166  
167

Vision therapy is a sequence of prescribed activities typically performed on a daily basis at home and weekly in-office, and is directed toward an individual patient's deficient skills. Visual skills are practiced under conditions that provide the patient with feedback. The feedback, along with a gradual increase in the demand of the activities as improvement occurs, enables the patient to improve visual functions such as visual acuity, fixation, accommodation, and vergence skills.

168  
169  
170  
171  
172  
173  
174  
175  
176  
177  
178  
179

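### The office-day patching rule is meant to equalise the two arms but leaves the active arm at least 15 minutes short per visit

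*Protocol*

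**What the plan says.** Protocol section 3.1 defines both arms by the same patching dose. The active arm's definition opens "Two (2) hours of daily patching combined with 30 minutes of daily near activities at" home and goes on "home, 30 minutes of daily at-home active vision therapy, and a weekly 45 minute in"-office session; the control arm's has the same structure. Section 3.2 prescribes 2 hours at home in both arms on days without a visit and forbids any increase.

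Office days are treated differently. Section 3.2.1 gives the reason: "In order to equalize patching time between the two groups the following changes to the patching" schedule are made. Active patients then patch for 1 hour at home and controls for 2 hours. Section 3.1.7 gives the same instructions for the first visit and for every later office day. Section 3.1.4 says that controls wear no patch during their session, and describes the purpose of the schedule more loosely: "to have similar amounts of patching times between the groups".

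For the active arm, section 3.1.2 does not fix how long the patch is worn in the office: "The amount of time the patient wears a patch during the in-office therapy session will be" determined by the category and phase of therapy. The details are left to the Manual of Procedures.

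**The concern.** Patching is the shared background on which active and control vision therapy are compared. The sponsor saw that office sessions could upset the balance and wrote a rule to restore it. The rule takes an hour of home patching from the active arm in exchange for a session of only 45 minutes. Even a session patched from start to finish cannot repay the hour, so the number chosen misses the purpose given for it. On office days the active arm also cannot reach the 2 hours by which section 3.1 defines it.

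At stake is a small systematic difference in assigned patching dose between the arms, in a trial whose question is the effect of the therapy added to patching.

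**Working it through.** The protocol gives no office-day total to reproduce, so the check is direct arithmetic on its instructions.

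**Inputs**
- Active arm, home patching on an office day: 60 min (3.2.1, 3.1.7)
- Control arm, home patching on an office day: 120 min (3.2.1, 3.1.7)
- Session length, both arms: 45 min (3.1)
- Patch wear in the session: 0 min for controls (3.1.4); *m* min for active, with 0 ≤ *m* ≤ 45 (3.1.2)
- Home patching on other days, both arms: 120 min (3.2)
- Office visits: 16, one per week (3.1)

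**Office day**
- Control: 120 + 0 = 120 min
- Active: 60 + *m* ≤ 60 + 45 = 105 min
- Shortfall: 120 − (60 + *m*) = 60 − *m* ≥ 15 min
- Equality would need *m* = 60, which is longer than the session.

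**Whole treatment period, session fully patched (*m* = 45)**
- Shortfall: 16 × 15 min = 240 min = 4 h
- Over 16 weeks, controls are assigned 16 × 7 × 2 h = 224 h. Active patients are assigned 16 × (6 × 2 h + 1 h) = 208 h at home plus 16 × 0.75 h = 12 h in the office, 220 h in all. The gap is 4/224 = 1.8%.
- Sections 3.1 and 3.2 continue patching through the 17-week examination. Over 17 weeks with 16 office days, controls are assigned 17 × 7 × 2 h = 238 h and active patients (238 − 16) + 12 = 234 h. The gap is 4/238 = 1.7%.

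**If part of the session is unpatched.** The shortfall is 60 − *m* per visit. At *m* = 30, an illustrative value, it is 30 min per visit, or 8 h over 16 visits. At *m* = 0 it is 60 min, or 16 h; this is an arithmetic bound and not an expected value.

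**With 75 minutes at home instead of 60**
- Active office-day total: 75 + *m* ≤ 75 + 45 = 120 min, so the 2-hour limit holds for every possible *m*.
- Shortfall: 120 − (75 + *m*) = 45 − *m*, which is 0 at *m* = 45 and 15 min smaller than under the present rule at every other value.

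**The case against.** The strongest reply is that this is a matter of wording. Section 3.1.4 asks only for similar patching times, and 105 against 120 minutes arguably meets that. No tolerance is set, and the rule does move the arms closer: without it, active patients would have 120 + *m* minutes against 120. One hour is easy to teach, and a round number is an ordinary simplification. Nothing shows that a gap of this size would change acuity, power or the conclusion. Most of this stands and is why the point is minor. It does not rescue the stated aim of equalising in 3.2.1, and 75 minutes comes closer to that aim than 60 at every level of patching in the session.

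A second reply is that section 2.1 speaks of a one-hour visit, so a patch worn throughout would give 60 + 60 = 120. But section 3.1.2 ties patch wear to the therapy session, which is 45 minutes. The visit also includes the diplopia query and acuity testing of each eye (4.2.1), which both arms undergo.

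In the other direction, a reader might infer that the true gap is well above 15 minutes. Vergence is one of the three therapy categories (3.1.2). Section 1.2 describes later stages as binocular: "Those children with no stereopsis would not be able to perform the activities in the later stages of therapy utilizing binocular vision". In section 3.1.3, "The Home Therapy System program will have therapy for vergence", and home therapy is patched except when "using the HTS software, which is performed without the patch". This suggests some unpatched office time, but the protocol does not say how much, and home use does not settle what happens in the office. Only the 15 minutes is established.

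A reader might also infer that unpatched home vergence work further lowers the active arm's dose. It does not: section 3.1.3 states the exception, and section 3.2 prescribes the 2 hours of patching separately.

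**Conclusion.** The point holds as a minor one. The office-day rule cannot equalise assigned patching: the active arm is at least 15 minutes per visit below the control arm, 4 hours over 16 visits, about 1.8% of the dose assigned over 16 weeks or 1.7% over 17. Any excess over that depends on unpatched session time that the protocol does not quantify.

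This rests on two assumptions: that patch wear in the office is confined to the 45-minute session, and that instructions are followed as written, since these are assigned and not observed doses.

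A reader might infer that the imbalance threatens the primary comparison. The documents do not support that. The gap is small and falls on the active arm. Provided that more patching does not worsen the outcome, it could slightly dilute a benefit of active therapy but could not create one.

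**What to change.** In sections 3.1.4, 3.1.7 and 3.2.1, change the active arm's home patching on office days from 1 hour to a fixed 75 minutes. The total then stays within 2 hours whatever the session contains, in keeping with the ban on increases in section 3.2. The arms are equal if sessions are fully patched, and the gap shrinks by 15 minutes otherwise.

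The cost is a slightly less round figure for parents to remember. It remains one constant instruction for every office day, with no new data to collect. Tailoring home time to each session's patched minutes is not worth doing: it would make therapists time patch wear and give families a changing figure, with a risk of instruction errors out of proportion to the gap.

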## 644 **3.3 Home Calendar Logs**

645

646 Parents will record the amount of time the patient wore the patch at home each day.  
647  
648 The calendars will be brought to the weekly office visits and a summary of the data will be  
649 entered onto the study website, along with other data collected at therapy visits.  
650  
651 At each visit, the logs will be reviewed by the therapist and an assessment of patching  
652 compliance recorded on the Follow-up Examination Form.  
653

655 **4.1 Follow-up Schedule**

656

657 All patients will have the following study visits:

- 658 • Weekly office visits  $\pm$  4 days for 16 weeks for administration of in-office vision therapy
- 659 • 17-week masked outcome visit  $\pm$  1 week

660 **4.2 Testing Procedures**661 **4.2.1 Weekly In-Office Vision Therapy Visits**662 The following activities/testing will be performed at the weekly office visits in the specified  
663 order:

- 664 • Binocular diplopia query
  - 665 ○ If a patient reports the onset of constant diplopia, treatment will be discontinued. If
  - 666 diplopia has resolved at the next week's office visit, therapy will be reinstated;
  - 667 however, anti-suppression therapy will not be performed for those assigned to
  - 668 Active vision therapy
- 669 • Measurement of visual acuity in each eye by the eETDRS testing protocol on the  
670 Electronic Visual Acuity Tester
  - 671 ○ The right eye is tested first, then the left eye
  - 672 ○ Testing is performed without cycloplegia with spectacles (if worn)
- 673 • In-Office Vision Therapy
  - 674 ○ Active or Control vision therapy based on randomization
- 675 • Completion of the therapy progress checklist

676

677 All patients will continue to have weekly in-office treatment sessions even if the visual acuity  
678 reaches 20/20 during the study.

679

680 All procedures at weekly vision therapy visits are permitted to be performed by a person who is  
681 unmasked to the patient's treatment assignment.682 **4.2.2 Scheduling of Weekly In-Office Vision Therapy Visits**

683 Ideally, treatment visits should be exactly 7 days apart; however, this will not always be possible.  
684 As such, we have established acceptable visit windows for the time between each in-office vision  
685 therapy visit. The acceptable window for each appointment is  $\pm$  4 days from the original  
686 targeted date (as calculated from the initial therapy session). Furthermore, no more than two  
687 appointments can be scheduled within a 7 day period and successive appointments must be more  
688 than 2 days apart.

689

690 Coordinators and Vision Therapists should consider creating a standing appointment time for  
691 each patient during the study. Care should be given to not schedule study patients back to back  
692 if possible to help minimize potential interaction between patients in different treatment arms.

693 **4.2.3 17-Week Masked Examination**

694 The following procedures will be performed at the 17-week Masked Outcome Examination. The  
695 visual acuity and stereoacuity tests need to be performed by a masked examiner. The order of  
696 procedures will be:

- 697 1. Binocular diplopia query

- 698 2. Measurement of visual acuity in each eye by the eETDRS testing protocol on the  
699 Electronic Visual Acuity Tester. (Must be performed by a masked examiner. The right  
700 eye is tested first.)  
701 3. Titmus Fly and Randot Preschool Stereoacuity Test (Must be performed by a masked  
702 examiner.)  
703 4. Ocular alignment by SPCT  
704 5. Ask the patient and the parent/guardian if they believe they were receiving active vision  
705 therapy or control therapy  
706 • This must be the last item completed.

707 **4.2.4 Unmasking of treatment assignment**

708 At the completion of the 17-week visit, the patient and parent will be told their treatment group  
709 assignment. Patients in the control group will be offered the opportunity to complete a course of  
710 active vision therapy that will be paid for by the study. To be paid by the study the  
711 parents/patient must decide to enroll in the vision therapy within 10 days after the completion of  
712 the 17-week masked examination.

713  
714

715

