### 248 Visit Schedule

249 Weekly in-office treatment visits ( $\pm$  4 days) for 16 weeks and a masked examination at 17 weeks

250 ( $\pm$  1 week).

251

252 At each weekly visit, the patient will be queried regarding diplopia, visual acuity will be

253 measured in each eye, and in-office therapy will be completed. Visual acuity measurements may

254 be completed by a person who is unmasked to the patient's treatment assignment. At the 17-

255 week masked examination the patient will be queried regarding diplopia, and visual acuity,

256 stereopsis, and ocular alignment will be measured. The visual acuity and stereoacuity tests will

257 be performed by a person who is masked to the patient's treatment assignment. Patients also will

258 be asked whether they believe they were receiving active or control vision therapy.

259

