## 457   **2.4 Examination Procedures**

### 458   **2.4.1 Historical Information**

459   Historical information to be collected will include: date of birth, gender, race, ethnicity, prior  
460   amblyopia therapy (e.g., glasses, patching, pharmacologic, filters, vision therapy), refractive  
461   correction, and history of allergy/intolerance to bandage adhesive.

462 **2.4.2 Clinical Testing for Enrollment**

- 463 1. Visual acuity in each eye (right eye first) is measured by the ATS single-surround eETDRS  
464 testing protocol on the Electronic Visual Acuity Tester. The protocol for conducting the  
465 visual acuity testing is described in the ATS Testing Procedures Manual. Aspects of the  
466 testing protocol that are specific to this study are indicated below:
- 467 • Testing must be done without cycloplegia (with spectacles, if worn) no more than 7 days  
468 prior to randomization.
  - 469 • Because the patient needs to be wearing spectacles that provide best visual acuity to be  
470 enrolled, trial frames/phoropter with a different correction cannot be used to measure  
471 acuity at enrollment.
  - 472 • If the patient has difficulty with the acuity testing, often he or she will perform better  
473 when the testing is repeated. At the investigator's discretion, acuity can be retested on  
474 the same or a subsequent day to assess eligibility.
- 475 2. Ocular motility examination
- 476 • Measurement of predominant alignment by Simultaneous Prism and Cover Test (SPCT)  
477 in primary position at distance and near.
  - 478 • Testing must be done without cycloplegia (with spectacles if worn) no more than 7 days  
479 prior to randomization
- 480 3. Ocular examination as per investigator's clinical routine to rule out a cause for reduced visual  
481 acuity other than amblyopia
- 482 ➤ if performed within prior 6 months, does not need to be repeated at time of  
483 enrollment.
- 484 4. Binocularity testing (without cycloplegia): Titmus Fly and Randot Preschool Stereoacuity  
485 test
- 486 5. Cycloplegic refraction using cyclopentolate 1% as per investigator's usual routine
- 487 ➤ if performed within prior 6 months, do not need to repeat at time of enrollment

488 **2.5 Randomization of Eligible Patients**

489  
490 Assuming that visual acuity in the amblyopic eye on the better of the initial or repeat tests is  
491 20/40 to 20/100, inclusive, and acuity in the sound eye is 20/25 or better, the patient will be  

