## 1018 **8.3 Safety Analysis**

1019

1020 Safety data consisting of the number and proportion of patients in each treatment group  
1021 experiencing the following events will be compiled and included in all reports to the DSMC:

- 1022       • Loss of 2 or more lines in sound eye visual acuity from baseline to the 17-week masked  
1023       exam  
1024       • Development of diplopia at any time during treatment and whether it has resolved by the  
1025       17-week masked exam  
1026       • Development of a new ocular deviation and whether it has resolved by the 17-week  
1027       masked exam

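### The 17-week cover test is the one examiner-judged test at that visit with no masking requirement, yet it can feed a safety item tabulated by arm

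*Protocol*

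**What the plan says.** **17-week visit (Protocol 4.2.3).** The opening rule is that the "visual acuity and stereoacuity tests need to be performed by a masked examiner". In the ordered list, item 2 (visual acuity) and item 3 (stereoacuity) each repeat the requirement. Item 4, "Ocular alignment by SPCT", has none. Item 5, the last, asks child and parent which therapy they believe was given.

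**Synopsis (1.3, Visit Schedule).** The synopsis draws the same line. It lists that "stereopsis, and ocular alignment will be measured" at 17 weeks along with acuity, but the next sentence names only the acuity and stereoacuity tests as those that must "be performed by a person who is masked to the patient's treatment assignment".

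**Safety reporting (8.3).** "Safety data consisting of the number and proportion of patients in each treatment group" with each listed event goes into every DSMC report. The third of three events is "Development of a new ocular deviation and whether it has resolved by the 17-week" masked exam.

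**Other alignment measurements.** SPCT is done at enrolment, before randomization (2.4.2). The weekly visits (4.2.1) schedule a diplopia query, acuity, therapy and a checklist, but no alignment test. SPCT is scheduled again in the observation phase at 13 and 52 weeks (5.3) and at the outcome examination of control non-responders who take active therapy (6.5).

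**The concern.** Calling a small or intermittent deviation on a cover test depends on what the examiner sees. An examiner who knows the arm may look harder, or call a borderline case differently, in one arm than in the other. The treatments give grounds for an expectation. Vergence and anti-suppression work are categories of active in-office therapy (3.1.2), and vergence software is part of active home therapy (3.1.3).

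New deviation is one of only three safety events the DSMC will see by arm, and the protocol treats it as a real risk (7.2.1 and 7.2.4). If ascertainment differs by arm, an imbalance may reflect who did the test, or a true imbalance may be blunted. The protocol protects stereoacuity, a secondary outcome read minutes earlier at the same visit, and gives no reason for leaving this test out.

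**Working it through.** **1. Which 17-week measurements are protected (4.2.3)**

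| Item | Who judges the result | Masked examiner required? |
|---|---|---|
| 1. Diplopia query | Child's report | No |
| 2. Visual acuity | Examiner-administered test | Yes |
| 3. Stereoacuity | Examiner-administered test | Yes |
| 4. Alignment by SPCT | Examiner's observation | No |
| 5. Treatment guess | Child's and parent's report | No |

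Within this visit, SPCT is the only examiner-judged test without the condition. No other section adds it.

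**2. How much of the safety item rests on this test**

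- Enrolment SPCT comes before randomization, so it is only the reference.
- Weekly visits have no scheduled alignment test, and in any case "All procedures at weekly vision therapy visits are permitted to be performed by a person who is" not masked to the arm.
- The 17-week SPCT is therefore the only scheduled alignment test after randomization within the randomized phase.
- Deviations can also come to light earlier, through the parent and investigator (7.2.1) or during treatment (7.2.4, item 3). Section 8.3 allows for this by asking whether a deviation has resolved by 17 weeks.

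The 17-week SPCT is thus a natural source for deviations not noticed before and for the resolution status of those that were. It is not the sole source of the count.

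**3. Illustration of size**

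The protocol gives no rate of new deviation and no SPCT sensitivity, so there is no figure to reproduce. The one input taken from it is 222/2 = 111 children per arm (8.1). The rest is assumed: the same true rate p in both arms, with probability of detection s1 in one arm and s0 in the other.

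Expected counts are 111 × p × s1 and 111 × p × s0. The apparent risk ratio is s1/s0. The apparent difference is p × (s1 − s0). The standard error of an arm difference at rate p is sqrt(2 × p × (1 − p)/111).

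| p | Standard error | 95% vs 75% detected | 90% vs 60% detected |
|---|---|---|---|
| 3% | 2.3 points | 3.2 vs 2.5 cases, 0.6 points | 3.0 vs 2.0 cases, 0.9 points |
| 5% | 2.9 points | 5.3 vs 4.2 cases, 1.0 point | 5.0 vs 3.3 cases, 1.5 points |
| 10% | 4.0 points | 10.5 vs 8.3 cases, 2.0 points | 10.0 vs 6.7 cases, 3.0 points |
| Apparent risk ratio | | 0.95/0.75 = 1.27 | 0.90/0.60 = 1.50 |

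For p = 5%: sqrt(2 × 0.05 × 0.95/111) = 0.029.

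In every row the bias is smaller than one standard error. To reach one standard error at p = 5%, about 0.029 × 111 = 3.2 calls would have to change in one arm. If these were all missed cases, that is 3.2 of 111 × 0.05 = 5.6 true cases, more than half, and nothing in the protocol suggests so large an effect.

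**The case against.** The strongest reply is that this is a deliberate and reasonable priority. The protocol masks the 17-week efficacy tests and leaves open a safety item that is neither a primary nor a secondary outcome. Section 8.3 compiles numbers and proportions and attaches no test, threshold or decision rule. The text does not say SPCT will be done unmasked. It follows directly after two masked tests, in a visit titled a masked examination, and families are told the assignment only once the visit is complete. The same examiner may well do all three tests. All of this stands, and it limits the weight of the point. It does not supply the missing condition.

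A second reply is that masking this one test removes only part of the problem, because deviations noticed during treatment are found by people who may know the arm. That also stands, and the fix has to allow for it.

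Several stronger readings are tempting, and the document does not support them:

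- A reader might infer that alignment is never tested again after enrolment except at 17 weeks. Sections 5.3 and 6.5 schedule it later; the statement holds only for the randomized phase.
- A reader might infer that the whole new-deviation count comes from this reading. Sections 7.2.1, 7.2.4 and 8.3 show that it need not.
- A reader might infer that SPCT is the only unmasked examiner-administered measurement in the trial. Weekly acuity, which feeds the rate-of-improvement analysis (8.7.2), may also be unmasked.
- A reader might infer a direction from the vergence training. Knowing the arm could lead an examiner to over-call or to under-call, so no direction follows.

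**Conclusion.** The point holds as a small, avoidable gap in safety ascertainment. The 17-week SPCT has no masking requirement, nothing excludes the child's therapist from doing it, and its result can enter a table by arm that the DSMC will read.

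The size and direction of any bias cannot be derived from the protocol. The risk ratios of 1.27 and 1.50 rest wholly on the assumed detection probabilities. In absolute terms the assumed scenarios shift the difference by 0.6 to 3.0 points, each less than its standard error. The reason to act is that the bias would be systematic, would affect a table built on few events, and costs little to prevent.

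A reader should not carry this over to efficacy. The primary outcome and the 17-week acuity and stereoacuity outcomes are read by a masked examiner and are unaffected. This is an optional improvement and does not threaten the trial's conclusions.

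**What to change.** - **Section 4.2.3, item 4, and the synopsis (1.3, Visit Schedule):** require the 17-week SPCT to be done by an examiner unaware of the assignment, and not by the child's therapist. This can be the masked examiner already present for items 2 and 3, or an investigator kept unaware of the arm until the examination is complete.
- **Section 8.3:** report by arm, as separate rows, deviations found unmasked during treatment and deviations found at the masked 17-week SPCT. The change to item 4 does not mask mid-treatment detection, and one pooled count would hide that.

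**Cost.** Two short changes of text for the test, one for the table, and a record of how each deviation came to light. There is no added test, visit or burden for the child. At some sites the masked examiner must be qualified for SPCT, or the investigator must stay unaware of the arm, which may be awkward where the investigator has managed the child during treatment. The feasibility phase already assesses the success of masking (1.3), so it is a convenient place to try the arrangement.
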